7.3.2.3 Criteria for Disease Progression

Table 7-3 Criteria for disease progression of subjects enrolled into the study

| Disease status at enrolment | Disease progression criteria | Reference |
|-----------------------------|--|------------|
| CML-CP | Progression to CML-AP or CML-BP at any time during the study Or WBC count that rises to $> 20.0 \times 10^9 / L$ ($> 20,000 / mm^3$) on two occasions at least 2 weeks apart (after first 4 weeks of K0706 therapy) in a subject Or | [REDACTED] |

| | | |
|---------------|--|------------|
| | Platelet count that rises to $> 600 \times 10^9/L$ ($> 600,000/mm^3$) on two occasions at least 2 weeks apart (after first 4 weeks of K0706 therapy) in a subject Or Loss of CHR (in the absence of a CyR) confirmed by complete blood counts done 4 weeks apart Or Loss of MCyR Or Death | |
| CML-AP | Development of confirmed BP Or Loss of previous major haematological response over a 2 week period Or No decrease from baseline levels in percentage blasts in peripheral blood or bone marrow on all assessments over a 4 week period (monitored at least every week) Or Death | [REDACTED] |
| CML-BP | Increasing blasts in peripheral blood or bone marrow over a 4 week period (monitored at least every week) Or Death | [REDACTED] |

Note: For subjects wherein rapid disease progression is observed (beyond the aforementioned criteria) and subject safety is a concern, the subject can be discontinued at Investigator's discretion

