- All study procedure related events occurring post consent and prior to first IMP administration will be recorded as Non Treatment Emergent Adverse Events (Non TEAEs).
- Disease progression as defined in Section 7.3.2.3 or as per clinical judgement of Investigator is not considered as an adverse event in the study, unless it leads to hospitalization or death in which case it should be reported as SAE. Subjects with disease progression should be discontinued from the study and their EoT visit be performed at the earliest.

For SAEs:

- SAE reporting period for safety surveillance begins after the subject consents for the study and continues until 30 days from end of treatment visit or last dose of IMP will be reported if it is considered related to IMP/study procedure by the investigator.
- All SAEs occurring prior to receiving the first dose of study drug will be recorded as Non TEAEs. Site as well as Sponsor/Sponsor's designee will comply with any additional reporting requirements of the EC/IRB and applicable local regulations.
- All deaths occurring in the study will be reported as SAEs to the Sponsor. Site as well as Sponsor/Sponsor's designee will comply with any additional reporting requirements of the EC/IRB and applicable local regulations.

Follow up of unresolved AEs: Any AE/SAE unresolved at end of study visit will be followed until resolution or until the event is stabilized as per medical judgement of the investigator.

Events Not to Be Considered as AEs/SAEs

Medical, baseline, pre-dosing conditions present at the initial study visit (i.e.: screening visits) that do not worsen in severity or frequency during the study, are defined as Baseline Medical Conditions and are not to be considered AEs.

For criteria pertaining to disease progression please refer to guidance in the aforementioned text on Additional guidance on AE/SAE reporting.

Suspected Unexpected Serious Adverse Reactions and Unexpected Adverse Reactions

Any suspected adverse reaction that is serious, unexpected, and considered to be related to drug exposure is defined as a SUSAR.

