used. When central laboratory data is not available, then data from the local laboratory will be used for the analysis. [REDACTED]

[REDACTED]

Molecular Response:

Molecular response is assessed using quantitative PCR (qPCR) based on the amount of BCR-ABL protein in the blood and is presented below in Table 2.

[REDACTED]

[REDACTED]

[REDACTED]

[REDACTED]

[REDACTED]

Cytogenetic, molecular, and hematologic responses will be summarized [REDACTED]

[REDACTED]

[REDACTED]

[REDACTED]

Criteria for Molecular Responses

[REDACTED]

Cytogenetic, molecular, and hematologic responses will be summarized [REDACTED]

[REDACTED]

Cytogenetic, molecular and hematological responses [REDACTED] will be presented [REDACTED]. The response rate at a specific time point is defined as the number of subjects who achieved the response at that time point divided by the total number of subjects in the treatment group. [REDACTED]

[REDACTED] The hematological

response will be summarized only for subjects with CML-AP and BP.

A separate summary will be provided for the best cytogenetic and molecular responses by achieved and maintained responses during the study period. The assessment for the achieved response includes all subjects who entered the study without the specific response. The assessment for the maintained response includes subjects who entered the study with the specific response.

By-subject listings of pharmacodynamic parameters will be provided for the safety analysis set. A by-subject listings will be provided for subjects who had disease progression.

Time to CCyR/MMR (in weeks), defined as the date of first documented CCyR/MMR - date of randomization + 1 divided by 7 will be summarized descriptively using number of subjects, mean, SD, median, minimum, maximum and quartiles.

Duration of CCyR/MMR, defined as the time between the date of the first documented MMR to the earliest date of confirmed loss of MMR or progression to accelerated phase (AP)/BP, or CML-related death will be summarized descriptively. The duration of CCyR/MMR (in weeks) is calculated as (end date or censoring date of CCyR/MMR - date of first CCyR/MMR + 1)/7.

All analysis will be conducted separately for all CML subjects and CML-CP subjects.

Further analyses for efficacy may be performed by dose group, stage of CML, resistance or intolerance, and mutational status.

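### The end events for duration of CCyR/MMR in the SAP match neither the response measured nor the protocol's progression criteria, so a responder who progresses can have no end event

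*SAP*

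**What the plan says.** The definition is in the SAP's efficacy text, whose own heading is redacted; it stands between Section 10 (Medications) and Section 13 (Survival). It reads "Duration of CCyR/MMR, defined as the time between the date of the first documented MMR", and the interval runs "to the earliest date of confirmed loss of MMR or progression to accelerated phase (AP)/BP, or CML-related death". The formula given for weeks is "end date or censoring date of CCyR/MMR - date of first CCyR/MMR + 1)/7", with no visible rule for the censoring date. On population the SAP says "All analysis will be conducted separately for all CML subjects and CML-CP subjects", so accelerated- and blast-phase subjects are included.

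The protocol makes duration of response a secondary endpoint in all Part C subjects (Section 7.3.1.4.2). It defines progression by phase at entry in Table 7-3 (Section 7.3.2.3). The first criterion for chronic phase is "Progression to CML-AP or CML-BP at any time during the study". Others include WBC and platelet rises, loss of MCyR, and "Loss of CHR (in the absence of a CyR) confirmed by complete blood counts done 4 weeks apart". For blast phase the only criterion other than death is "Increasing blasts in peripheral blood or bone marrow over a 4 week period (monitored at least every week". On what follows progression, Section 7.5.3.1 says "Subjects with disease progression should be discontinued from the study and their EoT visit be performed at the earliest".

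SAP Section 13 counts a PFS event at documented progression requiring withdrawal, or at death from any cause, and otherwise censors at the last response assessment.

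**The concern.** The end of a response should be marked by the loss of that response, or by an event that the protocol itself treats as failure of treatment. Here the list looks as if it was written for molecular response in chronic phase and then applied to a joint CCyR/MMR parameter in all phases. A subject with CCyR but no MMR cannot lose MMR. A Cohort C subject is already in blast phase, so a first transition to AP or BP is not available. A subject who progresses leaves study treatment and assessment, so the second observation that a confirmed loss seems to require may not be taken.

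Such subjects would have no end date and would need a censoring date instead. If that date is at relapse, the censoring is informative: the subjects removed from the risk set are those whose response has just failed. In a single-arm study with no formal testing, durability is one of the main things a reader weighs beside the response rate.

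**Working it through.** The plan gives no figure to reproduce. The check has two parts.

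**1. Table 7-3 against the SAP's three end events**

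| Cohort | Covered | Partly covered | Not covered |
|---|---|---|---|
| A (CP), 6 criteria | progression to AP or BP | death (SAP: CML-related only) | WBC rise; platelet rise; loss of CHR without a cytogenetic response; loss of MCyR |
| B (AP), 4 criteria | development of confirmed BP | death | loss of MaHR; no decrease in blasts |
| C (BP), 2 criteria | none | death | increasing blasts |

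Totals: 2 of 12 covered, 3 partly, 7 not covered (2 + 3 + 7 = 12). Two of the seven hardly concern a CCyR/MMR responder. Loss of CHR applies only without a cytogenetic response, and no decrease in blasts describes a subject who has not responded. That leaves five that matter (7 - 2 = 5): WBC rise, platelet rise, loss of MCyR, loss of MaHR and increasing blasts.

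Two subjects, following the text as written:

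- *Cohort C responder whose blasts rise over 4 weeks.* This is progression under Table 7-3. The subject is discontinued and is a PFS event. For duration there is no new AP/BP transition and no death, so the subject ends only if a confirmed loss of MMR is on record.
- *Cohort A subject with CCyR but not MMR who loses MCyR.* This is progression and a PFS event. For duration, loss of CCyR or MCyR is not listed, and loss of MMR cannot occur. No end event is available.

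On confirmation: Table 7-3 asks for none for loss of MCyR. After discontinuation, follow-up collects survival and anticancer therapy (Protocol Sections 7.3.1 and 7.3.2.5). While a subject is on study, Section 7.5.2.2 lets marrow samples go to 6-monthly intervals after CCyR on two assessments. A repeat is therefore not assured.

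**2. Illustration of size**

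All inputs are assumptions, because the documents give none: exponential durations with true median m of 12, 18 or 24 months; a share c of relapses (20% or 40%) censored at relapse; Kaplan-Meier estimation. Censoring a random share c of events at their own times multiplies the apparent hazard by (1 - c), so

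- true 24-month value: S = 0.5^(24/m)
- apparent value: S* = 0.5^((1 - c) × 24/m)
- apparent median: m/(1 - c)

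| m (months) | True S(24) | Apparent, c = 20% | Excess | Apparent, c = 40% | Excess | Apparent median, c = 40% |
|---|---|---|---|---|---|---|
| 12 | 0.5^2 = 25.0% | 0.5^1.6 = 33.0% | 8.0 | 0.5^1.2 = 43.5% | 18.5 | 12/0.6 = 20 |
| 18 | 0.5^1.333 = 39.7% | 0.5^1.067 = 47.7% | 8.0 | 0.5^0.8 = 57.4% | 17.7 | 18/0.6 = 30 |
| 24 | 0.5^1 = 50.0% | 0.5^0.8 = 57.4% | 7.4 | 0.5^0.6 = 66.0% | 16.0 | 24/0.6 = 40 |

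The excess runs from about 7 to about 19 points. For scale, with an assumed 10 to 15 responders, √(p(1 - p)/n) is √(0.40 × 0.60/15) = 12.6 points at p = 0.40, n = 15, and √(0.50 × 0.50/10) = 15.8 points at p = 0.50, n = 10. At c = 20% the bias is below one standard error; at c = 40% it is at or above one.

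**The case against.** The strongest reply is that the loss limb does most of the work. MMR is a far deeper response than MCyR, so an MMR responder who loses MCyR would be expected to have lost MMR already, and confirmed loss of MMR is an end event in every cohort. A fall from CCyR to PCyR keeps MCyR, so it is not progression and does not take the subject off study before a repeat. This stands, and it narrows the group affected. It does not help the CCyR responder without MMR, or the subject whose first evidence of loss coincides with progression.

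Second, the censoring rule and the meaning of confirmed are not visible, and the End of Treatment visit might supply the repeat sample. The duration is said to be summarized descriptively, and the time-to-event method in SAP Section 6.1 is redacted. If end and censoring dates were simply pooled in a descriptive summary, the effect would depend on which date is used for censoring. This also stands, and it is why the overstatement is given as a tendency.

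Third, this is a secondary endpoint, and progression still shows in PFS and in the SAP's listing of subjects who progressed. That is true, but neither corrects the duration summary.

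A reader might infer three stronger things that the documents do not support:

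- *That transformation is not protocol progression in any cohort.* Table 7-3 lists it for chronic phase, and lists development of BP for accelerated phase. Only the blast-phase row lacks it.
- *That the transformation limb is impossible in Cohort B.* AP to BP is a new transition and can occur. Even in Cohort C the SAP does not say whether a return to blast phase after a response would count.
- *That MCyR and MaHR durations are affected in the same way.* The visible sentence defines duration for CCyR/MMR only, and much of the surrounding text is redacted.

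**Conclusion.** The definition is wrong as written, in a limited form. Loss of CCyR does not end a duration named for CCyR. The transformation limb is one of several protocol criteria in Cohorts A and B and matches none in Cohort C. Only CML-related death counts, where Table 7-3 and the PFS definition count any death. The same subject can therefore be a PFS event and be discontinued for progression without an end event for duration.

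The likely direction is overstatement. It rests on these subjects being censored rather than ended, and on a method that respects censoring. The size is unknown. The 7 to 19 points at 24 months are an illustration under assumed exponential durations, Kaplan-Meier and a 20-40% share, not an estimate for this trial. The conclusion does not extend to MCyR or MaHR duration.

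**What to change.** Replace the end-event sentence in the SAP with a rule stated separately for each response whose duration is reported. Duration ends at the first of:

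- loss of that response, dated at the first assessment that shows it, if the loss is later confirmed or if the subject leaves before a repeat can be taken;
- disease progression under Table 7-3 for the subject's cohort;
- death.

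Censor all others at the last response assessment, which is the rule SAP Section 13 already uses for PFS.

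The cost is SAP wording and the matching programming. The downside for the sponsor is that reported durations become shorter.

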13 SURVIVAL

Overall survival is defined as the time from date of first dose to the date of death from any cause. Subjects who are alive at the time of the analysis data cut-off will be censored at the date of last contact.

Progression free survival is defined as the time from date of first dose to the date of earliest occurrence of documented disease progression requiring withdrawal from the study or death from any cause. Any subject who has neither progressed nor died will be censored on the date of his/her last response assessment (hematological, cytogenetic or molecular).

Overall survival and progression-free survival rates will be summarized [REDACTED]

[REDACTED]

[REDACTED]

[REDACTED]

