Treatment beyond 60 months will be considered, provided the Investigator considers that the subject is benefiting from K0706 therapy. Subjects who continue to receive K0706 beyond 60 months will be followed up for safety, survival and response assessments. Information about subject's survival and disease response will be collected at the follow up visits every 3 months in these subjects.

Medical Care of Subjects after the End of Treatment Visit:

After a subject has completed the study or has withdrawn early from the study, usual treatment (as per the local standards of care) may be administered, if required, in accordance with the study center's generally accepted medical practice and depending on the subject's individual medical needs. The Sponsor will not have any role to play in further treatment and the treatment regimen followed will be outside the purview of the study protocol. Information about subject's survival and anticancer therapies will be

collected every 3 months for approximately 60 months from the subject's first dose, by telephone contact, medical record review, and/or study center visits until death, withdrawal of consent, or the end of the study, whichever comes first. This information will be documented by the study center personnel in the subject's source documents and the electronic data capture system

Schematic of the design is presented in Figure 6-1 Schematic for the Study: PART B

- A. If medically warranted, subjects may be admitted to the study center overnight on Cycle 1 Day 1.
- B. The last observation and assessments for each cycle will coincide with the Day 1 of next cycle. The window period for Day 1 of every cycle in ± 3 days

[REDACTED]

[REDACTED]

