[REDACTED] Note: The last observation/evaluations for each cycle may coincide with the Day 1 of the next cycle e.g., Cycle 6 day [REDACTED] observation may coincide with Cycle 7 day 1). [REDACTED] samples will be collected on the day of study visit from Cycle 3 onwards. Subjects will return for a follow up- visit approximately 30 days after the last K0706 administration.

Subjects will remain on study treatment for approximately 60 months (i.e.: 5 years from 1st K0706 dosing), or until intolerance, subject withdraws from the study, or progression of disease. Subjects who discontinue the study will be followed up for survival (survival assessment includes information about subject survival and anticancer therapies) every 3 months (\pm 2 weeks) after the IMP discontinuation till 60 months from their first dose of K0706 or until death, withdrawal of consent, or the end of the study, whichever comes first.

Treatment beyond 60 months will be considered, provided the Investigator considers that the subject is benefiting from K0706 therapy. Subjects who continue to receive K0706 beyond 60 months will be followed up for safety, survival and response assessment. Information about subject's survival and disease response will be collected at the follow up visits every 3 months (\pm 2 weeks) in these subjects.

Subjects who experience a toxicity and recover, may be treated (at the Investigator and subject discretion) at the same dose or next lower dose level until disease progression or other events requiring dose reduction exist. [REDACTED]

[REDACTED] For additional details on dose delays and reduction refer to Section 7.4.2.1.

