7.7.3 Evaluation of Safety

The safety and tolerability profile of K0706 in subjects treated on this study will be assessed by physical examination, AEs, vital signs (including blood pressure [systolic and diastolic], pulse rate, respiratory rate, and temperature), ECG, and clinical laboratory tests (including hematology, coagulation, cardiac troponin, clinical chemistry, and urinalysis). The timing of these assessments will be according to the schedule of assessments Section 11.2

Adverse events will be assessed based on the NCI CTCAE v5.0 and categorized as SAEs or AEs. The relationship of AEs to K0706 will be assessed by the Investigator per the protocol-defined criteria for attribution assessment.

Subject performance status will be assessed using the ECOG performance status scale.

Subject survival will be followed every  months (± 2 weeks) by telephone contact, medical record review, and/or study center visits wherein information about subject survival and anticancer therapies will be collected after the end of treatment until death, withdrawal of consent, or the end of the study, whichever comes first.

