3.2 PART C

Part C is a multicenter, phase 2, single arm, open-label study of oral Vodobatinib in subjects with Ph+ CML (CP, AP and BP) who have resistance and/or intolerance to ≥ 3 prior TKIs one of which includes ponatinib. Subjects must have documented evidence of intolerance and/or primary (never had a response) or secondary resistance (loss of a response) following standard or high dose TKI therapy (refer Inclusion Criteria # 3).

Eligible subjects will enter the study center [REDACTED] on Day 1 to receive the first administration of Vodobatinib [REDACTED] and will complete the required assessments and sample collections, [REDACTED]. [REDACTED]

[REDACTED] Subjects may be admitted a day prior to Cycle 1 Day 1 dosing and if required stay overnight at the study center on Cycle 1 Day 1, based on Investigator's discretion. Subjects will complete the assessments on Cycle 1 Day 2 and may remain in the study center overnight for observation, at the discretion of the Investigator. Subjects will return for follow-up assessments ([REDACTED]) in Cycle 1 [REDACTED]. [REDACTED].

Cycle 2 will have similar [REDACTED] sample collections on Day 1, and subjects will be required to return to the study center [REDACTED] for [REDACTED] follow-up assessments. From Cycle 3 onwards, subjects will only be required to return to the study center once every [REDACTED] months ([REDACTED]). [REDACTED]. Note: The last observation/evaluations for each cycle may coincide with the Day 1 of next cycle e.g., Cycle 6 Day [REDACTED] observation may coincide with Cycle 7 Day 1). [REDACTED] samples will be collected on the day of the study visit from Cycle 3 onwards.

Subjects will remain on study treatment for approximately 60 months (i.e.: 5 years from 1st Vodobatinib dosing), or until intolerance, subject withdraws from the study, or progression of disease. Subjects who discontinue the study will be followed up for survival (survival assessment includes information about subject survival and anticancer therapies) every [REDACTED] (± 2 weeks) after the Vodobatinib discontinuation till 60 months from their first dose of Vodobatinib or until death, withdrawal of consent, or the end of the study, whichever comes first. Subjects enrolled in Part C at [REDACTED] of Vodobatinib ([REDACTED]) will remain in the study, but will not be considered for the statistical analysis for Part C.

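### Survival contact ends at month 60 only for subjects off drug and the readable OS rule sets no common cut, so OS beyond month 60 may be biased upward

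*SAP*

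**What the plan says.** SAP section 13 gives the endpoint: "Overall survival is defined as the time from date of first dose to the date of death from any cause". Its censoring rule for survivors is: "Subjects who are alive at the time of the analysis data cut-off will be censored at the date of last contact". The next statement on method, "Overall survival and progression-free survival rates will be summarized", runs into redacted lines. Protocol 7.8.5 leaves the OS and PFS censoring rules to the SAP, so this is where a limit would be expected.

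How long survival is tracked depends on treatment status:

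- **Off drug, Part C.** Protocol 7.3.1 has contact every 3 months "after the IMP discontinuation till 60 months from their first dose of K0706", or to death, withdrawal of consent or end of study if earlier. SAP 3.2 agrees: "after the Vodobatinib discontinuation till 60 months from their first dose of Vodobatinib or until death, withdrawal of consent".
- **Off drug, Part B.** Protocol 6.3.1 sets the same 60-month limit.
- **On drug past month 60.** This requires the investigator's judgement that the subject is benefiting. Then, for Part C (7.3.1): "Subjects who continue to receive K0706 beyond 60 months will be followed up for safety, survival and response assessment". For Part B (6.3.1): "Subjects who continue to receive K0706 beyond 60 months will be followed up for safety, survival and response assessments".
- **A different rule for Part C.** Protocol 7.7.3 collects survival "after the end of treatment until death, withdrawal of consent, or the end of the study, whichever comes first", with no 60-month limit.

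Protocol 9.5 ends the study at the last visit of the last subject, so early enrollees can be observed beyond month 60. Protocol 5.2 shows that Part B subjects had been treated by 18 July 2019. Sixty months from that date is July 2024. The data cut-off date is not readable.

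**The concern.** Kaplan-Meier assumes that a censored subject has the same later risk of death as those still followed. Under the 60-month rule, every living off-drug subject is censored together at month 60, while those selected for continuing benefit stay at risk. Subjects come off drug for progression, intolerance or withdrawal, so being censored at that point is probably linked to prognosis.

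OS is a named secondary endpoint of Part C, which is single-arm and which the protocol calls pivotal. With no comparator, the absolute curve will be taken at face value. An inflated tail would overstate long-term survival. It could also move the median, but only if more than half of the subjects are alive at month 60.

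**Working it through.** The plan states no OS rate, event count or power, so there is no figure to reproduce. The size is shown over a range. **All rates below are assumptions**, and so is the use of Kaplan-Meier.

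Notation, with time in years: a = death rate on drug, b = death rate off drug, d = rate of stopping drug, p = share of those alive at month 60 who are still on drug.

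**Check 1: nobody stops drug after month 60.** Take S(60) = 0.60 and a = 0.05.

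- True S(84) = S(60) × [p·exp(−2a) + (1−p)·exp(−2b)]
- Estimated S(84) = S(60) × exp(−2a) = 0.60 × 0.9048 = 0.543

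| b | b:a | True S(84), p = 0.3 / 0.5 / 0.7 | Excess of the estimate |
|---|---|---|---|
| 0.05 | 1:1 | 0.543 / 0.543 / 0.543 | 0 |
| 0.10 | 2:1 | 0.507 / 0.517 / 0.527 | 0.036 / 0.026 / 0.015 |
| 0.20 | 4:1 | 0.444 / 0.473 / 0.501 | 0.098 / 0.070 / 0.042 |

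**Check 2: stopping at a constant rate.** Subjects off drug by month 60 are censored at 60. Those who stop later are censored when they stop.

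- True S(t) = exp(−(a+d)t) + [d/(a+d−b)] × [exp(−bt) − exp(−(a+d)t)]
- Estimated S(84) = S(60) × exp(−2a)

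Example with a = 0.05, b = 0.20, d = 0.20, so that d/(a+d−b) = 4:

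- S(60) = 0.2865 + 4 × (0.3679 − 0.2865) = 0.612
- True S(84) = 0.1738 + 4 × (0.2466 − 0.1738) = 0.465
- Estimated S(84) = 0.612 × 0.9048 = 0.554, an excess of 0.089
- Share of those alive at month 60 still in the risk set just after it = 0.2865/0.612 = 47%

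| a | b | d | True S(84) | Estimated S(84) | Excess |
|---|---|---|---|---|---|
| 0.05 | 0.05 | 0.20 | 0.705 | 0.705 | 0 |
| 0.05 | 0.10 | 0.20 | 0.604 | 0.645 | 0.041 |
| 0.05 | 0.20 | 0.10 | 0.557 | 0.617 | 0.060 |
| 0.05 | 0.20 | 0.20 | 0.465 | 0.554 | 0.089 |
| 0.05 | 0.20 | 0.30 | 0.407 | 0.508 | 0.102 |
| 0.05 | 0.25 | 0.242 (2% per month) | 0.384 | 0.493 | 0.109 |
| 0.03 | 0.15 | 0.181 (1.5% per month) | 0.589 | 0.675 | 0.086 |

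A simulation of 400,000 subjects for each of the first five rows agrees to within 0.002. It also gives the true S(60) every time (for example 0.613 against 0.613), so estimates up to month 60 are unaffected.

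**The case against.** Much of the opposing case stands and limits the point.

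- **Redaction.** A reader might infer that the SAP does not truncate OS. Only the readable text can be said to lack a cut. A month-60 limit or a fixed landmark could sit in the hidden lines of SAP 13, and Kaplan-Meier is nowhere named in readable text.
- **Section 7.7.3.** If it governs, the asymmetry disappears in Part C, and a cap there would discard valid deaths. The 60-month rule would remain in Part B. SAP 13 is not limited to one part in its readable text, although only Part C names OS as an endpoint.
- **What the tail represents.** A reader might infer that the curve after month 60 describes only subjects still benefiting. That goes too far. Its level still carries S(60) from every subject, and only the later death rate comes from the on-drug group.
- **Size.** No document gives a mortality ratio. Protocol 7.1 describes poor survival in this population. With few alive at month 60, the absolute excess shrinks: at a = 0.20, b = 0.40, d = 0.242 it is 0.172 against 0.134 at month 84, or 0.038.
- **Stopping after month 60.** The documents do not say what happens to survival contact then. If it continues, the estimate in the worked example becomes S(60) × S(24) = 0.612 × 0.862 = 0.527, and the excess falls from 0.089 to 0.062.
- **PFS.** A reader might extend the cap to PFS. Nothing here supports that. Progression is itself the PFS event, SAP 13 censors PFS at the last response assessment, and no PFS bias has been shown.

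None of this removes the status-dependent end of contact in 6.3.1, 7.3.1 and SAP 3.2, or the conflict with 7.7.3.

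**Conclusion.** The point holds conditionally. Wherever the 60-month limit applies, censoring at month 60 depends on treatment status, and the readable OS rule does not neutralize it. OS after month 60 is then biased upward if three things are true: Kaplan-Meier is used, the cut-off falls beyond month 60 for some subjects, and off-drug mortality exceeds on-drug mortality.

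At month 84 the excess is 0 at equal mortality, about 1.5 to 4 points at 2:1, and about 4 to 11 points at 4:1 to 5:1, all on assumed rates. OS is secondary and protocol 7.8 plans no formal testing, so no test or error rate is affected. The contradiction between 7.7.3 and the other Part C text needs no assumption and should be resolved in any case.

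**What to change.** 1. Reconcile protocol 7.7.3 with the Part C design text in the protocol summary, protocol 7.3.1 and SAP 3.2, so that one end of survival follow-up is stated. Also state what happens to survival contact when a subject stops drug after month 60.
2. Wherever the 60-month limit is kept, add a sentence to SAP 13: OS is administratively censored at 60 months from first dose for every subject, whether on or off drug. Show OS, with numbers at risk, to month 60 only, and list later deaths.
3. If all subjects are instead followed to the end of the study, no cap is needed.
4. Leave the PFS rule as it is on this point.

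The cost is one SAP sentence and one aligned protocol statement. Estimates up to month 60 do not change. The downside is that deaths after month 60 in on-drug subjects move from the curve to a listing. Following everyone to the end of the study avoids that loss but needs longer contact with off-drug subjects.
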